### **Reporting to Industry Partners**

All AEs and special situations, whether serious or non-serious, related or not related, following exposure to [REDACTED] medicinal product are to be documented by the investigator and recorded in the CRF and in the subject's source records. Investigators must record in the CRF (if consistent with Sponsor policies) or MedWatch form their opinion concerning the relationship of the AE to a [REDACTED] medicinal product.

All (serious and non-serious) AEs reported for a [REDACTED] medicinal product should be followed-up in accordance with clinical practice.

### **SAEs, Adverse Events of Special Interest and Special Reporting Situations**

All serious adverse events that have not resolved by the end of the study, or that have not resolved upon discontinuation of the subject's participation in the study, must be followed until any of the following occurs:

- The event resolves
- The event stabilizes
- The event returns to baseline, if a baseline value/status is available
- The event can be attributed to agents other than the study drug or to factors unrelated to study conduct
- It becomes unlikely that any additional information can be obtained (subject or health care practitioner refusal to provide additional information, lost to follow-up after demonstration of due diligence with follow-up efforts)

The Sponsor and the Investigator) will transmit all SAEs, AEs of Special Interest and special situations following exposure to a [REDACTED] product under study using MedWatch Form 3500A in accordance with Section 9 of this Exhibit B, Transmission Methods, in English within twenty-four (24) hours of becoming aware of the event(s).

All follow-up information for serious adverse events that are not resolved at the end of the study or by the time of patient withdrawal must be reported directly by the PRINCIPAL INVESTIGATOR, within 24 hours becoming aware, [REDACTED] using the Serious Adverse Event Report

All available clinical information relevant to the evaluation of a related SAE, AEs of Special Interest, serious ADR or special situation is required.

- The INSTITUTION and/or PRINCIPAL INVESTIGATOR is responsible for ensuring that these cases are complete and if not are promptly followed-up. A safety report is not considered complete until all clinical details needed to interpret the case are received. Reporting of follow-up information should follow the same timeline as initial reports.
- Copies of any and all relevant extraordinary (not including routine initial or follow-up ICSR submission) correspondences with regulatory authorities and ethics committees regarding any and all serious adverse irrespective of association with the J&J Product under study, are to be provided to the COMPANY using a transmission method in Section 9 within 24 hours of such report or correspondence being sent to applicable health authorities.

### Non-Serious AEs

All non-serious AEs should be reported to COMPANY according to the timeframe outlined in the Agreement section entitled Reporting of Data.

### PQC Reporting

A PQC may have an impact on the safety and efficacy of the product. Timely, accurate, and complete reporting and analysis of PQC information from studies are crucial for the protection of patients, investigators, and the COMPANY, and are mandated by regulatory agencies worldwide. The COMPANY has established procedures in conformity with regulatory requirements worldwide to ensure appropriate reporting of PQC information. Lot and/or Batch #s shall be collected or any reports failure of expected pharmacological action (i.e., lack of effect). The product should be quarantined immediately and if possible, take a picture.

All initial PQCs involving a J&J medicinal product under study must be reported to the COMPANY by the PRINCIPAL INVESTIGATOR within 24 hours after being made aware of the event. The J&J contact will provide additional information/form to be completed.

If the defect for a [REDACTED] medicinal product under study is combined with either a serious adverse event or non-serious AE, the PRINCIPAL INVESTIGATOR must report the PQC to the COMPANY according to the serious adverse event reporting timelines. A sample of the suspected product should be maintained for further investigation if requested by the COMPANY.

## 8 Statistical Considerations and Evaluation of Results

### 8.1 Sample Size Considerations

#### 8.1.1 Sample Size and Power Estimate

The sample size determination is based on the primary endpoint of the study, the composite response rate. Composite response rate is defined in Section 3 and below in Section 8.3.2.

Based on historical control data, the null hypothesis is a 15% composite response rate. Simon's two-stage minimax design will be used. The null hypothesis that the true response rate is 15% will be tested against a one-sided alternative. In the first stage, 14 patients will be accrued. If there are 2 or fewer composite responses in these 14 patients, the study will be stopped. Otherwise, 10 additional patients will be accrued for a total of 24 patients. The null hypothesis will be rejected if 8 or more responses are observed in 24 patients. This design yields a type I error rate of 0.025 and power of 80.2% when the true composite response rate is 40%.

#### 8.1.2 Accrual Estimates

Based on our historical data, we estimate that approximately 15% of all mCRPC patients will meet the definition of treatment-emergent small cell NEPC (t-SCNC) as outlined in the Eligibility criteria in Section 3 of the protocol. We estimate an accrual rate of approximately 1.5 patients per month, and estimated accrual duration of approximately 18 months.

### 8.2 Interim Analyses and Stopping Rules

An interim analysis for safety and efficacy will be conducted after 14 patients are enrolled and have completed treatment. Criteria for efficacy stopping rule are outlined above in Section 8.1.1. With respect to interim safety analysis, if more than 33% (5 or more patients) experiences a Grade  $\geq 3$  treatment-related AE in cycle 1, excluding anemia or clinically insignificant laboratory abnormality, study accrual will be halted and alternative dose level and/or schedule may be investigated following safety analysis and protocol amendment.

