## Abstract

Title	A Phase 2 Study of Apalutamide Plus Cetrelimab in Patients with Treatment-Emergent Small Cell Neuroendocrine Prostate Cancer
Study Description	Phase 2 single arm, Simon two stage evaluation of the combination of apalutamide plus cetrelimab in patients with mCRPC and histologic and/or genomic evidence of treatment-emergent small cell neuroendocrine prostate cancer who have previously progressed on at least one prior androgen signaling inhibitor. The primary study endpoint is composite response rate as defined by PSA50 response and/or objective response by RECIST 1.1 criteria.
Phase of Study	Phase 2
Investigational Products	Apalutamide, Cetrelimab
Study population	Male, adult (18 years of age and older) patients with metastatic castration resistant prostate cancer (mCRPC) with disease progression (PD) on at least one second generation androgen signaling inhibitor, including abiraterone acetate, apalutamide, darolutamide, and/or enzalutamide and evidence of treatment-emergent small cell neuroendocrine cancer (t-SCNC). All races/ethnicity are included.
Primary Objective	To determine the composite response rate as defined by achieving one or more of the following at any time point during study treatment: 
 
• PSA50, decline from baseline in serum PSA of <math>\geq 50\%</math>, confirmed by repeat measurement <math>\geq 4</math> weeks later
 
• Objective response by RECIST 1.1 criteria
 

Secondary Objectives	
 
1. To determine safety of the combination as determined by CTCAE version 5.0
 
2. To determine the median radiographic progression-free survival by PCWG3 criteria
 
3. To determine the PSA50 and PSA90 response proportion achieved
 
4. To determine the median PSA progression-free survival
 
5. To determine the median overall survival
 
6. To determine the objective response rate and median duration of response by RECIST 1.1 criteria
 

Sample Size	N = 24 patients.

Duration of Study Treatment	Participants may continue study treatment from the time of treatment initiation until confirmed radiographic PD per PCWG3/RECIST 1.1 criteria, unequivocal clinical progression, unacceptable toxicity, or patient withdrawal, whichever occurs first – for a maximum of 24 months.

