## 3 Study Design

### 3.1 Characteristics

This is a phase 2, single arm, Simon's two-stage evaluation of the combination of apalutamide plus cetrelimab in patients with mCRPC and histologic and/or genomic evidence of treatment-emergent small cell neuroendocrine prostate cancer who have previously progressed on at least one prior androgen signaling inhibitor. The primary study endpoint is composite response rate as defined by PSA50 response and/or objective response by RECIST 1.1 criteria.

A planned interim safety and efficacy analysis is planned after 14 patients are treated (see Section 8).

[figure not shown]

Figure 3.1 Study Schema

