### 3.2 Sample Size

A total of 24 patients will be enrolled over an accrual period of approximately 18 months.

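### Section 8.2 ties a cycle-1 safety rule to 14 patients finishing treatment, leaves that trigger undefined, and no readable text states the accrual hold that the two-stage design implies

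*Combined protocol and SAP*

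**What the plan says.** Section 8.2 sets one formal interim look for both purposes: "An interim analysis for safety and efficacy will be conducted after 14 patients are enrolled and have completed treatment". For efficacy it refers back to Section 8.1.1: "If there are 2 or fewer composite responses in these 14 patients, the study will be stopped". The next sentence there reads: "Otherwise, 10 additional patients will be accrued for a total of 24 patients". For safety it counts patients with a Grade 3 or higher treatment-related event in cycle 1, with anaemia and clinically insignificant laboratory findings left out. At five or more, "study accrual will be halted and alternative dose level and/or schedule may be investigated following safety analysis and protocol amendment".

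Section 3.1 words the trigger differently, "A planned interim safety and efficacy analysis is planned after 14 patients are treated (see Section 8", and so points to Section 8 for the detail. The Abstract allows treatment "for a maximum of 24 months". Section 3.5 lists many reasons for ending treatment, and two years of therapy is only one of them. Section 2.2 counts a response at any time until treatment ends.

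On timing, Section 8.1.2 says: "We estimate an accrual rate of approximately 1.5 patients per month, and estimated accrual duration of approximately 18 months". Section 3.2 says: "A total of 24 patients will be enrolled over an accrual period of approximately 18 months". Section 3.7 puts primary completion at about month 24.

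Appendix 2 adds continuous review at monthly site committee meetings, DSMC review of serious events at meetings every six weeks, a report to the DSMC if Grade 3 or 4 rates are raised, and steps to follow if the investigator chooses to hold enrolment. The only explicit halt to accrual in the readable text follows a crossing of the safety threshold. The schema, Figure 3.1, was not available to this review.

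**The concern.** The safety rule needs 28 days of data per patient, but it is formally read only once the last of 14 patients has finished treatment. If the text is followed as written, a fifth qualifying event among the first 14 has no formal consequence until then.

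For futility, the stage-1 cut-off cannot be dated. Treatment could be complete when a patient stops for any reason or only after two years of therapy, and Section 3.1 says merely that the patients have been treated. A two-stage design saves patients only if stage 2 waits for stage 1. That wait has to be inferred from the word order of Section 8.1.1, and its end point is unclear.

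**Working it through.** **1. The plan's own design.** Stage-1 responses X1 follow Bin(14, p) and stage-2 responses X2 follow Bin(10, p). The probability of rejecting is the sum over x = 3 to 14 of P(X1 = x) × P(X2 ≥ 8 − x).
- p = 0.40: 0.802, which reproduces the stated 80.2%.
- p = 0.15: 0.0194, inside the stated 0.025.
- Stopping at stage 1, P(X1 ≤ 2): 0.648 at 15% and 0.040 at 40%.
- Expected N under the null: 14 + 10 × (1 − 0.648) = 17.5.

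**2. Calendar.** Inputs are the accrual rate (8.1.2), the 28-day cycle (5.1), the 24-month maximum (Abstract) and a month of 30.44 days. The rate implied by 24 patients in 18 months, 24/18 = 1.33, is shown as a variant.

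| Event | 1.5/month | 1.33/month |
|---|---|---|
| Patient 14 enters | 14/1.5 = 9.33 | 10.5 |
| Cycle-1 data on all 14 complete (+ 28/30.44 = 0.92) | 10.25 | 11.42 |
| Latest possible look (entry + 24) | 33.33 | 34.5 |
| Patient 24 enters if there is no hold | 24/1.5 = 16.0 | 18.0 |

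The largest possible gap for the safety rule is 33.33 − 10.25 = 23.1 months.

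**3. More typical gaps.** Entries are evenly spaced. Time on treatment is assumed exponential, capped at 24 months, and the look comes when the last of the 14 is off treatment. The documents give no treatment duration for this regimen in this disease, so a range is used. The 3.25-month value is the median in the cetrelimab monotherapy study of mixed solid tumours (Section 1.5). The 3.0-month value is the median time to progression on platinum in Section 1.2. The 2- and 6-month values are assumptions on either side.

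| Median duration (months) | Median gap after cycle-1 data, 1.5/month | Look after patient 24 would enter, 1.5/month | Same, 1.33/month |
|---|---|---|---|
| 2 | 4.7 | 38% | 28% |
| 3.0 | 18.94 − 10.25 = 8.7 | 76% | 66% |
| 3.25 | 9.7 | 82% | 73% |
| 6 | 18.4 | 99% | 98% |

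The gap is long even for short treatment because the trigger waits for the last of 14 patients.

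**4. What the safety rule loses.** P(at least 5 of 14) is 0.9%, 13% and 42% at assumed cycle-1 event rates of 10%, 20% and 30%. Suppose an event is known at day 28 of that patient's cycle 1. At 1.5/month, a fifth event in patient 12 or earlier is then known before patient 14 enters, since 12/1.5 + 0.92 = 8.92 is below 9.33. That covers 56% of crossings at a 20% rate and 66% at 30%.

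**5. Accrual without a hold.** If all 24 are in before the look, expected N under the null is 24 instead of 17.5, about 6.5 patients more. If the stage-1 rule is still applied, type I error remains 0.0194. If it is ignored and only the final rule of 8 or more in 24 is used, type I error is 0.0199 and power 0.808. The cost is patient exposure, not a false-positive risk above the stated level.

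**6. A hold released at a third confirmed response.** Three responses make the stopping condition impossible, so release at that point changes no decision and power stays at 80.2%. The hold runs until all 14 are off treatment only when fewer than 3 respond: 4.0% of trials at a true rate of 40%, 64.8% at 15%. Waiting for all 14 takes a median of about 4.7 + 0.92 = 5.6, 9.7 + 0.92 = 10.6 and 18.4 + 0.92 = 19.3 months for median durations of 2, 3.25 and 6 months.

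**7. An earlier fixed futility date.** Suppose a share f of stage-1 responders is confirmed by that date. Passing stage 1 then needs at least 3 confirmed. Power at 40% becomes 78.7%, 75.6%, 70.1% and 61.7% for f = 0.9, 0.8, 0.7 and 0.6. The documents give no value for f.

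**The case against.** The strongest reply is that much of this is already in the plan. Section 8.1.1 is sequential, so a hold is inherent in it, and a third response logically ends the stage-1 question. This stands: the defect is that neither the hold nor its end point is stated, not that the design allows straight-through accrual. Because Figure 3.1 was not available, the absence of a stated hold is established only for the readable text.

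Four stronger readings are tempting, and the documents do not support them.
- *Safety goes unwatched until the look.* Appendix 2 provides continuous and monthly review, DSMC oversight and notification of raised rates, and it foresees a voluntary enrolment hold at any time. What is missing is any application of the 5-of-14 rule in that period.
- *Sections 3.1 and 8.2 set rival cut-offs.* Section 3.1 is a summary that defers to Section 8. The wording needs aligning, but the main fault is the undefined term in 8.2.
- *The accrual plan leaves about two months for a hold (18 − 16.0).* Both planning figures are approximate, and at 1.33/month the slack is nil. No conclusion here rests on it.
- *The safety rule will probably be crossed.* Section 1.6 reports Grade 3 or higher rash in 37.0% of 27 patients, and a 37% rate would give a 64% chance of crossing. That figure is not limited to cycle 1 or to treatment-related events. Table 5.1 also gives every patient antihistamine and montelukast prophylaxis in the first two cycles. It does not supply the cycle-1 rate.

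The treatment durations are assumptions. The late trigger and the missing definition do not depend on them; the size of the typical gap does.

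**Conclusion.** The point holds and should be fixed. The only numeric safety rule is read later than its data require: at most 23.1 months later, and typically about 5 to 18 months later under the assumed durations. Month 33.3 is a ceiling, not a forecast. The stage-1 trigger has no executable definition, and the implied hold is unstated. If accrual did not wait, the two-stage saving would be lost in many or nearly all trials, depending on treatment duration. The stated power reproduces, and no claim is made that type I error exceeds 0.025.

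**What to change.** 1. Separate the safety reading from the efficacy look. Evaluate the existing cycle-1 rule, threshold unchanged, when patient 14 completes cycle 1, or as soon as a fifth qualifying event occurs among the first 14. The same 14 patients are counted, so the probability of crossing does not change.
2. Use one defined stage-1 cut-off in Sections 3.1 and 8.2: all 14 off treatment, or a third confirmed composite response, whichever comes first. State that accrual holds after patient 14 until stage 1 has been passed and the safety rule has been read on all 14. This matches the response window in Section 2.2 and keeps the 80.2% power.
3. Revise the accrual and primary completion estimates in Sections 3.2, 3.7 and 8.1.2 to allow for the hold.

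The cost is an amendment, an explicit hold and later planning dates; N and the response boundaries stay as they are. The safety condition adds at most about 0.9 months to the hold. Long holds fall mainly on trials with fewer than 3 responses, which are heading for futility. An earlier fixed futility date would shorten them, but it is not recommended without its own power calculation, given the losses in step 7.

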### 8.3 Analyses Plans

#### 8.3.1 Analysis Population

The safety population is defined as any patients who received at least one dose of protocol therapy on study.

The analysis population for the primary composite response endpoint includes all patients evaluable for composite response, defined as possessing either a Screening PSA  $> 2$  ng/mL and/or measurable disease by RECIST 1.1 criteria.

The analysis population for the time-to-event efficacy endpoints including progression-free survival, PSA progression-free survival, and overall survival are all patients who receive at least one dose of protocol therapy. Criteria for censoring for each of the study endpoints is listed below in Section 8.3.3.

The analysis population for correlative endpoints include all patients who receive at least one dose of protocol therapy who have evaluable correlative sample/data.

#### 8.3.2 Primary Analysis (or Analysis of Primary Endpoints)

The composite response rate is the primary endpoint of the study, defined as:

- $\geq 50\%$  decline from baseline PSA (defined by C1D1 value), confirmed by repeat measurement  $\geq 3$  weeks later AND/OR
- Objective tumor response by RECIST 1.1 criteria AND/OR

The composite response rate along with 95% confidence interval will be reported.

### 8.3.3 Secondary Analysis (or Analysis of Secondary Endpoints)

Secondary Objective 1 Analysis: AEs will be recorded and severity-graded using CTCAE version 5.0. Clinically significant laboratory, physical exam, scan, and ECG abnormalities will be captured as AEs. The frequency and severity of AEs will be descriptively reported on a per-patient analysis.

Secondary Objective 2 Analysis: The median radiographic progression-free survival determined by PCWG3 criteria

Secondary Objective 3 Analysis: PSA50 and PSA90 response are defined as above, a  $\geq 50\%$  and  $> 90\%$  decline from baseline in serum PSA, respectively, confirmed by repeat measurement  $\geq 4$  weeks later. The PSA50 and PSA 90 response proportions will be reported along with 95% confidence interval for each study cohort, for the subset of PSA-evaluable patients (serum PSA  $\geq 2$  ng/mL at baseline).

Secondary Objective 4 Analysis: Median progression-free survival will be determined for each cohort as from the date of first dose of protocol-defined therapy, using Kaplan-Meier product limit method. Progression is defined as per Section 7.1.4. The first scan time point demonstrating radiographic progression requires confirmatory scans performed  $\geq 4$  weeks after first scan time point to confirm progression. Patients who discontinue treatment for reasons other than those listed above (e.g. AE, patient withdrawal) will be censored by the date of last treatment.

Secondary Objective 5 Analysis: The median overall survival along with 95% confidence interval will be determined from the date of first dose of protocol-defined therapy until death from any cause, using the Kaplan-Meier product limit method. Patients will be followed for long-term survival as outlined in the Study Procedures. Patients who withdraw from study will be censored for analysis of overall survival using the date of study withdrawal.

Secondary Objective 6 Analysis: The objective response rate and median duration of response will be reported along with 95% confidence interval, for the subset of patients with measurable soft tissue disease by RECIST 1.1 criteria.

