## 2.3 Secondary Objectives and Endpoints

Secondary Objective	Endpoints	Time Frame
1. To determine safety of the combination of apalutamide and cetrorelimab	
 
Proportion of participants with treatment-related AEs, as graded by National Cancer Institute Common Terminology Criteria for Adverse Events (NCI CTCAE version 5.0)
 
	From initiation of study treatment until treatment discontinuation.
2. To determine the median radiographic progression-free survival by PCWG3 criteria	
 
Median progression free survival by PCWG3 criteria.
 
	From initiation of study treatment until radiographic progression by PCWG3 criteria or death, whichever occurs first.
3. To determine the PSA50 and PSA90 response proportion.	
 
<math>\geq 50\%</math> and <math>\geq 90\%</math> decline from baseline in PSA, respectively, confirmed by repeat measurement <math>\geq 4</math> weeks after first time point*
 
	From initiation of study treatment until maximal decline in serum PSA during study treatment.
4. To determine the median PSA progression-free survival.	
 
Median PSA progression-free survival by PCWG3 criteria.
 
	From initiation of study treatment until PSA progression by PCWG3 criteria or death, whichever occurs first.
5. To determine the median overall survival.	
 
Median overall survival from date of start of protocol treatment until death from any cause.
 
	From initiation of study treatment until death from any cause. (3 years)
6. To determine the objective response rate by RECIST 1.1 criteria	
 
Objective response rate by RECIST 1.1 criteria.
 
Median duration of response
 
	From initiation of study treatment until maximal percent decline from baseline in SLD of target lesions.

\* To be considered evaluable for this endpoint, patients must have baseline PSA level  $> 2$  ng/mL.

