### **Definition of Progressive Disease**

A composite definition of PD will be defined by first occurrence of any one of the following:

- Appearance of new metastatic lesions outside the bone
- New metastatic lesions on bone scan confirmed as described above
- Development of an indication for radiotherapy while on treatment
- Unequivocal progression of non-target lesions
- Global deterioration of health status requiring discontinuation of treatment without objective evidence of PD
- Development of an indication for non-protocol systemic therapy

Patients experiencing radiographic progression in the absence of clinical progression are allowed to remain on treatment until follow up scan confirms progression.

Note that PSA progression (as defined above) alone does not meet the criteria for progressive disease.

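### Section 8.3.3 analyses PSA progression-free survival (Objective 4) with a scan-based paragraph, leaves radiographic PFS (Objective 2) as a fragment, and censors deaths that Section 2.3 counts as events.

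*Combined protocol and SAP*

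**What the plan says.** Section 2.3 sets up two time-to-event endpoints besides overall survival. Objective 2 runs "From initiation of study treatment until radiographic progression by PCWG3 criteria or death, whichever occurs first". Objective 4 runs "From initiation of study treatment until PSA progression by PCWG3 criteria or death, whichever occurs first". Section 8.3.1 also names PSA-PFS separately from PFS and promises: "Criteria for censoring for each of the study endpoints is listed below in Section 8.3.3".

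Section 8.3.3 then gives:

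- Objective 2, in full: "Secondary Objective 2 Analysis: The median radiographic progression-free survival determined by PCWG3 criteria". There is no verb, estimator, confidence interval or censoring rule.
- Objective 4: "Secondary Objective 4 Analysis: Median progression-free survival will be determined for each cohort as from the date of first dose of protocol-defined therapy", by Kaplan-Meier, with progression taken from Section 7.1.4. It continues: "The first scan time point demonstrating radiographic progression requires confirmatory scans performed" at least 4 weeks later. The censoring rule is: "Patients who discontinue treatment for reasons other than those listed above (e.g. AE, patient withdrawal) will be censored by the date of last treatment".

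Section 7.1.4 defines PSA progression (under post-treatment PSA changes), target-lesion progression, PCWG3 bone progression and PFS (progression or death). It also has a composite list of progressive-disease events that ends: "Note that PSA progression (as defined above) alone does not meet the criteria for progressive disease". Section 6.3.6 follows patients for survival every 90 days after the last dose.

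**The concern.** The text filed under Objective 4 describes a different endpoint. An analyst who follows it literally would report a scan-based PFS under the PSA-PFS label. One who notices would have to choose the PSA-PFS estimator and censoring after seeing the data. For radiographic PFS, one patient can be an event or censored depending on which section is followed. In a single-arm study these medians are read against outside data, and PFS also enters the exploratory biomarker comparisons (Sections 2.4 and 8.3.4). The definitions should therefore be fixed beforehand.

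**Working it through.** The documents state no PFS median, event count or precision, so there is no plan figure to reproduce. The check is mainly a comparison of sections.

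**1. Endpoint against analysis, Objective 4.** Section 2.3: PSA progression or death. Section 8.3.3: progression shown on scans and confirmed on scans. The pointer to Section 7.1.4 does not settle it, because that section both defines progressive disease by PSA and says that PSA progression alone is not progressive disease.

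**2. Two readings.** If the paragraph belongs to Objective 4, its progression rule is the wrong one and Objective 2 has no method. If it is misplaced Objective 2 text, Objective 2 has a method and Objective 4 has none. Either way one endpoint lacks the censoring rule promised in Section 8.3.1. These are alternatives, so the two harms do not add.

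**3. Why the label matters.** Cycles are 28 days.
- PSA is due on day 1 of each cycle, so first at C2D1 = 28 days = week 4, then every 4 weeks.
- Scans (Section 6.1, footnote 6): C4D1 = 3 × 28 = 84 days = week 12; C7D1 = 6 × 28 = 168 days = week 24; C11D1 = 10 × 28 = 280 days = week 40; then every 4 × 28 = 112 days = 16 weeks. The window is −14 days, and earlier scans are allowed if clinically indicated.

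The two endpoints are read on different clocks and are not interchangeable.

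**4. Deaths after stopping.** Under Section 8.3.3, a patient who stops for an adverse event and later dies without recorded progression is censored at last treatment. Under Sections 2.3 and 7.1.4 that death is an event, and Section 6.3.6 collects it. Section 1.6 reports adverse-event discontinuation in 6/27 = 22.2% on the same combination.
- 24 × 6/27 = 5.3 patients.
- Exact 95% CI for 6/27: 8.6% to 42.3%; × 24 = 2.1 to 10.1 patients.

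This is an upper figure for adverse-event stops: Section 5.2 lets one drug continue when the other is stopped, and not every such patient dies without earlier recorded progression. The documents give no rate for withdrawals.

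**5. What counts as progression.** The composite list in Section 7.1.4 adds an indication for radiotherapy, an indication for other systemic therapy, and global deterioration without objective progression. It omits target-lesion growth, which the same section covers elsewhere. Section 2.3 asks for radiographic progression, and Section 7.1 for RECIST 1.1 with PCWG3 bone rules. A patient who stops because other systemic therapy is indicated, without radiographic progression, is an event under the list and censored under Section 2.3.

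**6. Effect of the censoring rule on radiographic PFS (simulation, all inputs assumed).** Assume exponential progression with median 3, 4 or 6 months, post-progression survival median 4, 8 or 12 months, 22.2% stopping early, no scans after stopping, and 200,000 patients per scenario. Shift in estimated PFS just before the week-24 scan, relative to complete follow-up:

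| Rule | Stops unrelated to progression | One in six related | All related |
|---|---|---|---|
| As written (last treatment) | at most 0.001 | 0.006 to 0.008 | 0.041 to 0.047 |
| Count every later death | +0.013 to +0.036 | not summarised | +0.030 to +0.081 |

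Censoring at last scan instead of last treatment changes the result by at most 0.005.

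**7. Effect of censoring PSA-PFS at last PSA (simulation, all inputs assumed).** Assume radiographic median 3, 4 or 6 months, post-progression survival median 8 months, PSA every 4 weeks, and PSA progression at twice the radiographic time. The PSA-PFS median with complete follow-up is about 24, 32 and 46 weeks. If PSA stops when radiographic progression is detected, the Kaplan-Meier median is roughly 75, 108 and 170 weeks. With 4 more weeks of PSA it is about 37, 60 and 106 weeks. Treatment ends at 24 months (about 104 weeks), so the longest of these would not be reached.

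**The case against.** The strongest reply is that this is an editorial slip. Sections 2.3, 7.1.4 and 8.3.1 already fix the PSA-PFS event, time origin and population, so a careful analyst would not use scans. That stands in part. A reader might infer that PSA-PFS is wholly undefined or that no PSA event could ever be counted; the documents do not support that. What is missing is a stated estimator, PSA-specific censoring and a confidence interval, in a section that points to conflicting text.

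Second, an endpoint may count death and still carry an explicit earlier censoring rule. That is a legitimate choice, and by step 6 the rule does little harm unless most stops are linked to coming progression. A reader might infer that censoring at last treatment materially biases radiographic PFS; that is not shown. The narrower point remains: Section 2.3 sets no on-treatment limit on death, so the sections disagree about the same patient.

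Third, the Section 7.1.4 pointer also reaches target-lesion progression and bone progression. A reader might infer that target-lesion growth is lost from the endpoint; it is absent only from the composite list.

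Fourth, it is tempting to state the error in weeks. Assumed models can make the scan-based median longer or shorter than the PSA-based one, depending on whether PSA progression leads or lags. The documents give no such relation, so no range in weeks should be quoted as the size of the error.

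**Conclusion.** The point holds as an internal inconsistency that should be corrected before analysis. The Objective 4 paragraph does not analyse the Objective 4 endpoint, Objective 2 has no stated method, and the censoring sentence and the composite progression list each conflict with the Section 2.3 definitions. No confidence interval is stated for either PFS median, although Objectives 5 and 6 have one.

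The stakes are moderate: two secondary, descriptive medians in 24 patients, with no test or decision attached. The primary composite response analysis is unaffected. The figure of about 5 patients assumes that the discontinuation rate in the earlier combination study carries over. That the paragraph is misplaced Objective 2 text is an inference from its content, not something the documents say.

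**What to change.** 1. Move the Kaplan-Meier paragraph to Objective 2. Define the event as RECIST 1.1 soft-tissue progression (including target-lesion growth), PCWG3 bone progression, or death. Report the non-radiographic events in the composite list separately.
2. Under Objective 4 write: PSA progression as defined in Section 7.1.4 or death; Kaplan-Meier from first dose; event-free patients censored at last PSA. Report how many are censored because treatment ended for radiographic progression. State that the median is overstated, possibly heavily or not reached, if PSA progression tends to follow radiographic progression.
3. Reconcile the censoring sentence with Section 2.3 by stating in advance whether deaths after stopping count, with one sensitivity analysis under the alternative. Replacing last treatment by last scan is optional, since it barely changes radiographic PFS.
4. Report both medians with 95% confidence intervals.

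The cost is wording and one extra sensitivity analysis, with no new visits, scans or changes to treatment rules. The medians may look less favourable. No death rule is free of bias, because no scans or PSA are scheduled after End of Treatment, although the note to Table 7.1 asks for every effort to document later progression.
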